**Table 1 eCRF Data Collection**

Variables	Enrollment visit	Post-enrollment follow-up visits
Demographics		
Age, gender, race/ethnicity, height	X	
Weight*	X	
Relevant Medical History		
Age at diagnosis of MF-CTCL	X	
Date of MF-CTCL diagnosis	X	
Method of diagnosis	X	
MF-CTCL TNMB classification*	X	
MF-CTCL TNMB classification change		X
MF-CTCL histology	X	
Malignancies and secondary malignancies	X	
Non-melanoma skin cancers	X	
Prior viral infections	X	
Atopic disorders	X	
Psoriasis	X	
Urticaria	X	
Mental disorders	X	
Family medical history	X	
Other relevant medical history	X	
Changes in medical history		X
Targeted MF-CTCL Treatments (Medication Use and Dosing)*		
Valchlor	X	X
Other MF-CTCL treatments	X	X

Variables	Enrollment visit	Post-enrollment follow-up visits
Healthcare utilization related to MF-CTCL (as assessed by physician)		
Hospital admissions ‡		X
Emergency room visits		X
Clinical Status (as assessed by physician)	X	X
Clinical Status Assessments*		
Composite Assessment of Index Lesion Severity	X	X
Modified Severity Weighted Assessment Tool	X	X
Physician's Global Assessment	X	X
Body Surface Area of disease	X	X
Patient-Completed Questionnaires§		
Visual Analogue Scale for pruritus	X	X
Skindex-29	X	X
Safety Measures**		
AEs and SAEs	X*	X
Reports of secondary exposures		X †

\*Included in pre-treatment data collection, which is performed at enrollment. All data must be completed as available.

†Includes collection of start and stop dates for each medication, including reasons for starting and stopping medications. Start and stop dates are also collected for Valchlor, including short gaps in treatment, such as drug holidays.

‡For each hospital admission, length of stay and primary admission and discharge diagnoses will be collected.

§To be completed by patients who can read and understand English and are able to self-complete the questionnaires based on the investigator's assessment. Patients who are unable to self-complete the questionnaires will not be excluded from the study.

\*\*Safety measures, which include AEs and SAEs, will be collected from the informed consent date and prospectively at every visit during the study and up to 30-days post-discontinuation of Valchlor during the study. Ongoing AE and SAE data will be collected through the end of study, regardless of Valchlor use. New AEs and SAEs that occur more than 30 days after discontinuation of Valchlor will be reported to Actelion US Drug Safety if investigator feels there is a possible causal relationship with Valchlor.

## ANALYSIS VARIABLE DEFINITIONS

This section describes the source of analysis variables and, where derivation is required, the derived variable algorithm. Many analysis variables are either directly reported by sites on the MedNet study database eCRF or are calculated automatically by the MedNet EDC system based on source variables entered by sites. Algorithms for derivation of these variables will not be included.

### Demographics and clinical characteristics at enrollment

Demographic information is reported on the Enrollment eCRF and will include age (at time of enrollment), gender, and race. Clinical characteristics are primarily collected on the Enrollment eCRF and will include height (in), weight (lbs), disease history (collected on the eCRF at enrollment), post-treatment response assessments, treatment history, pre-treatment (Valchlor) data, relevant medical history, safety information, and patient completed questionnaires (at enrollment).

### **Medical history at enrollment**

Relevant medical history categories at enrollment will be reported. The data are collected first as categories on the enrollment eCRF and then as a specific condition on the Relevant Medical History Log, as applicable. Medical history categorized as 'other' will be reported together as a separate category. The following categories will be reported:

- Secondary malignancies
- Non-melanoma skin cancer
- Prior viral infections
- Atopic disorders
- Psoriasis
- Urticaria
- Mental disorders
- Relevant family history (like lymphoma)
- Other malignancies specified
- Other relevant medical history

### **Other MF-CTCL Treatments**

Other MF-CTCL medications will be categorized by specific therapies (skin-directed therapies, systemic therapies and other) and identified by comparing the start/stop dates of the various medications/therapies recorded on the Other MF-CTCL Treatments Log with the date of enrollment from the Enrollment eCRF. A table summarizing pre-treatments and therapies that were stopped prior to enrollment will be included, as well.

Patients will be considered to be on other medications/therapies (specific for MF-CTCL). The data will include the medication/therapy start date either on the day of enrollment or before the day of enrollment and have either continued or stopped taking the medication after the day of enrollment. By this algorithm, patients who start a medication on the day of enrollment will be considered to be on that medication at enrollment, patients who start and stop a medication on the day of enrollment will be considered to be on that medication at enrollment, but patients who stop a medication on the day of enrollment will not.

### **Valchlor dosing regimens**

Valchlor dosing information (number of tubes per month) will be determined by using the data collected on the Valchlor Treatment Log. Sites will also record start and stop dates, reason for initiating therapy and reason for stopping. The number of tubes of Valchlor therapy dosed following initiation will be counted and the tubes per month will be computed as the total number of tubes divided by the months on Valchlor per the start and stop date. A sustained number of tubes will be defined with no change for 90 days.

### **Healthcare Resource Utilization**

Hospitalizations and ER visits that occur during the course of the study will be reported in a table summarizing the rate of hospitalizations and the rate of ER visits will be presented. Data will come from the Healthcare Resource Utilization module on the eCRF. The denominator will be based on the sum of follow-up time available for all subjects. Only hospitalizations and ER visits that occur post-enrollment will be included in the numerator. These will be reported separated as continuing Valchlor versus newly initiated Valchlor patients.

## **Patient Disposition and Reason for Discontinuation**

The number and percentage of patients discontinuing from the study, along with the number and percentages of the reasons for discontinuation will be presented in a table. In addition, a listing of all patient disposition, including completed patients and discontinued patients, will be provided.

## **Clinical Status Assessments / Response**

In order to capture the variety of response assessment methods (ie practice patterns) no individual method of determining response, either at enrollment or at follow-up, is mandated. A subjective categorical assessment of response will be included in addition to quantitative measures of response, but assessments that do occur must be captured during follow-up. Additionally, it is important to capture which methods were used at pre-treatment (prior to Valchlor) and post-treatment (after initiating Valchlor) to review the physicians evaluation for each patient treatment.. The possible methods for assessing response recorded on the eCRF are given below:

- Clinical Status (as assessed by physician) will be collected in one of 5 categories: complete response, partial response, stable disease, progressive disease, and relapse. A selection of Complete Response or Partial Response will be considered a response.
- Composite Assessment of Index Lesion severity (CAILS) score of 50% or more will be considered a response.
- Modified Severity Weighted Assessment Tool (mSWAT) score of 50% or more will be considered a response.
- Body Surface Area in Disease (BSA) score of 50% or more will be considered a response.
- Physician's Global Assessment (PGA) will be collected in one of 7 categories: completely clear, almost clear, marked improvement, moderate improvement, slight improvement, no change, worse. A rating of Moderate Improvement or better will be considered a response.
- Other (to be specified by physician on the eCRFs)

In cases where multiple clinical assessment / response measures are available for a particular patient-visit, the patient will be considered a responder if at least one of the measures indicates response.

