5.7.4 Clinical outcomes

The main clinical outcomes that will be analyzed are clinical response, as assessed by the physician, and MF-CTCL-related healthcare utilization, as assessed by the physician (e.g., hospitalizations and emergency room visits). Rates of on-study hospitalization and emergency room visits will be computed as the ratio of utilization counts divided by on-study days. Hospitalization-free survival will be computed using Kaplan-Meier estimates.

Because a wide variation in assessments of clinical response is expected, the clinician's subjective evaluation of response will be summarized in addition to reporting the proportion of responses among patients for whom specific tests were performed. The subjective response will be cross-classified by which assessments were used. The summary of response data is primarily a descriptive analysis to better understand how and when physicians define response, and it does not represent an estimate of the efficacy of any MF-CTCL treatment.

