5.7.6 Patient-completed questionnaires

The Skindex-29 is a questionnaire that results in three scales: emotions, symptoms, and functioning [Chren 1996, Chren 1997a, Chren 1997b, Chren 2001]. Appendix A shows the items in the Skindex-29 questionnaire and Appendix B describes the scoring of individual items to the 3 scales. To compute the scale, each item is first transformed to a linear 0–100 scale where responses of “Never”, “Rarely”, “Sometimes”, “Often”, and “All the time” are converted to values of 0, 25, 50, 75, and 100, respectively. Next, the mean of the non-missing items for each scale is computed to derive a scale score. Although missing data for individual items is allowed, no scale score will be computed if more than quarter of the items in the scale are missing.

The VAS for pruritus is a single value [Reich 2012] and is shown in Appendix C.

The MF/SS-CTCL questionnaire contains 12 questions [PatientsLikeMe 2016] and is shown in Appendix D.

At each study visit (1st, 2nd, etc.), the VAS for pruritus, the three scales of the Skindex-29 and the MF/SS-CTCL will be computed for patients who are and are not responders,

based on clinician assessment, at the time of that visit. These descriptive cross-sectional comparisons are intended to assess burden of disease in a Valchlor-treated cohort over time. The data related to all three questionnaires (VAS, Skindex-29, MF/SS-CTCL) will be collected on the QOL questionnaires.

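### In the questionnaire tables split by response, the SAP's any-one-measure rule makes responder status depend partly on how many optional tools were used, and it can contradict the physician's own rating

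*SAP*

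**What the plan says.** The SAP section Clinical Status Assessments / Response states that "no individual method of determining response, either at enrollment or at follow-up, is mandated". It lists physician clinical status, CAILS, mSWAT, BSA, PGA and a free-text 'other' category.

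- Physician status has five categories: "complete response, partial response, stable disease, progressive disease, and relapse". For this item, "A selection of Complete Response or Partial Response will be considered a response".
- For PGA, "A rating of Moderate Improvement or better will be considered a response".
- CAILS, mSWAT and BSA each have a 50% threshold.
- 'Other' has no threshold.

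When more than one measure is available at a visit, "the patient will be considered a responder if at least one of the measures indicates response". The section gives no order of precedence and no rule for measures that disagree.

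The SAP's Statistical Methods section stratifies the VAS and Skindex-29 summaries by response. It contains a second any-one rule that names VAS and Skindex-29 as the measures. It also says that a patient may fall in both categories within a quarter, depending on clinical status at different visits.

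For the questionnaire comparison, protocol 5.7.6 separates responders from non-responders "based on clinician assessment, at the time of that visit". Protocol 5.7.4 plans to summarize the clinician's subjective evaluation in addition to "reporting the proportion of responses among patients for whom specific tests were performed", and to cross-classify the subjective response by the assessments used.

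**The concern.** A rule that takes the best of whatever was measured is not the same rule at every clinic. A visit with one tool has one chance to be positive, and a visit with five has five. The protocol itself expects wide variation in assessment practice, so the number of tools will differ between sites and between visits.

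Tables 17aa, 17ab and 17b are meant to show symptom and quality-of-life burden in responders and non-responders. If the split is partly a record of assessment intensity, the groups stop meaning what their labels say. Visits the physician regards as stable, progressive or relapsed would then be averaged into the responder group, and a reader of the table could not tell.

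**Working it through.** **1. Where the flag is used.**

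| Output | Basis of response |
|---|---|
| Primary endpoint and sensitivity analysis (Tables 21, 21a) | BSA reduction from baseline of at least 50% |
| By-time BSA, ORR2, ORR4 (Tables 22 to 24) | Same BSA criterion |
| Tables 6a to 6c, Listing 8 | Each measure on its own |
| Tables 17aa, 17ab, 17b | Responder versus non-responder split |

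Only the last row needs one combined flag per visit. No table shell reports a composite responder percentage.

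**2. What the rule does.** Let R_j = 1 if tool j is positive at a visit. The flag is max(R_1, ..., R_k) over the k tools used. Adding a tool cannot lower a maximum, so a further tool can turn a non-responder into a responder but never the reverse. If physician status is progressive disease (R = 0) and PGA is moderate improvement (R = 1), the flag is max(0, 1) = 1, a response.

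**3. The definitions side by side.**

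| Source | Who is a responder |
|---|---|
| SAP, Clinical Status Assessments / Response | Any one of physician status, CAILS, mSWAT, BSA, PGA, other |
| SAP, Statistical Methods | Any one available measure, naming VAS and Skindex-29; the same section also refers to clinical status |
| Protocol 5.7.6 | Clinician assessment at that visit |

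These do not give one definition for the same tables.

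**4. Illustration of size.** The plan gives no figure to reproduce: neither a response rate per tool nor an agreement between tools. All inputs here are assumptions: each tool is positive at 40% of visits, and the latent scores are normal with a common correlation ρ. With t the 40% normal quantile,

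P(flag) = 1 − E_Z[(1 − Φ((t − √ρ·Z)/√(1 − ρ)))^k], with Z standard normal.

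| ρ | k = 1 | k = 2 | k = 3 | k = 4 | k = 5 |
|---|---|---|---|---|---|
| 0.5 | 40.0% | 56.1% | 65.0% | 70.7% | 74.7% |
| 0.7 | 40.0% | 52.2% | 58.8% | 63.1% | 66.2% |
| 0.9 | 40.0% | 46.9% | 50.6% | 52.9% | 54.7% |

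- One tool to two: gains of 16.1, 12.2 and 6.9 points.
- One tool to five: gains of 34.7, 26.2 and 14.7 points.

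If physician status is one of the k tools, the share of flagged visits that are negative on it is 1 − 0.40/P(flag). At ρ = 0.7 this is 1 − 0.40/0.522 = 23% with two tools and 1 − 0.40/0.662 = 40% with five.

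These are shares of visits. Tables 17aa, 17ab and 17b report n, mean, SD and range of VAS and Skindex-29. Turning misclassification into a shift in those means would need the score difference between concordant and discordant visits, which the documents do not give.

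**The case against.** **Scope.** A reader might infer that the main response results are inflated. The documents do not support that: the primary endpoint, by-time BSA analyses, ORR2 and ORR4 all rest on BSA reduction alone, and no shell reports an any-measure response rate. This objection stands in full.

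**Which rule governs the tables.** The Statistical Methods section mentions clinical status when explaining how a patient can appear in both groups, so it could be read as already sorting by physician status. That reading is possible, but the same section contains its own any-one rule. What stands is that the SAP is ambiguous; what does not follow is that the problem is absent.

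**Conflict with the protocol.** Protocol 5.7.6 says clinician assessment and does not name complete or partial response. Protocol Table 1 places CAILS, mSWAT, PGA and BSA under clinical status assessments, PGA is itself a physician rating, and protocol 5.7.1 leaves the definition of response to the SAP. Taking 5.7.6 to mean the physician's clinical status item is the natural reading, but not a stated definition.

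**Size.** The rates and correlations are invented for illustration, and nothing shows that five-tool visits occur. If the same physician completes status and PGA at one visit, agreement may be very high: at ρ = 0.95 the gain from one tool to five is about 10 points. How often a progression rating coincides with a positive tool is unknown.

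**Truth standard.** Protocol 5.7.4 calls the physician's evaluation subjective and the response summary descriptive, so calling the flag biased against it assumes a standard the plan does not claim. This is fair. The dependence on tool count, however, needs no such assumption.

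**Conclusion.** The point holds for the descriptive response-split questionnaire tables (17aa, 17ab, 17b) and no further. Applied as written, the any-one rule sorts visits partly by the number of tools used and allows a responder label at a visit the physician rates as progression or relapse. It departs from the classifier in protocol 5.7.6 on its natural reading, and the SAP does not define the split consistently.

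The direction follows from logic alone. The size is not known: about 7 to 16 points from one tool to two and 15 to 35 points from one to five hold only under the assumed 40% rate, equal rates across tools and equal correlation of 0.5 to 0.9. The effect on mean VAS and Skindex-29 scores has not been estimated. The SAP should be changed because the repair is cheap and uses data already collected, not because a headline result is at risk.

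**What to change.** Replace the any-one sentence in Clinical Status Assessments / Response, and align the responder sentence in Statistical Methods, so that both say the following. In every table split by response, a responder visit is one with a physician clinical status of complete or partial response at that visit. This is already the SAP's own response rule for that item.

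Report response on CAILS, mSWAT, BSA and PGA separately, each among visits where the tool was used. Cross-classify each against physician status, in line with protocol 5.7.4. Do not form a composite.

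The cost is a wording change in two SAP sections; no new data are needed. Visits with a tool score but no physician status would leave the response-split tables. Their number cannot be judged from the documents, so it should be reported beside the tables.

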## **Missing versus No Assessment**

For patients who do not have any assessments reported on the eCRF for a completed visit, the negative response for the assessment is required and collected to document the absence of the assessment. In addition, for patients that do not have at least 1 clinic visit during a quarter, an affirmative response that the patient is still under care by the site will be requested quarterly. Thus, missing data is not anticipated due to the eCRF requirements for responses and the absence of reported assessments can be interpreted the same as the absence of actual assessments.

## **Skindex-29 Questionnaire**

The Skindex-29 will be administered based on the questions and scoring algorithm found in Appendix A and Appendix B of the protocol. Each patient at each visit during the study will be asked to complete the Skindex-29 which comprises results in three scales; emotions,

symptoms, and functioning. No scale score will be computed if more than 25% of the items in the scale are missing.

### **VAS for Pruritus**

The VAS for pruritus is a single item and defined in the protocol Appendix C.

### **Exposure Definitions and Measures**

Start of observation is defined as date of enrollment.

End of observation is defined as End Of Study (EOS), which includes, adverse event, patient withdrew consent, patient lost to follow-up, physician's decision to withdraw or study completion, whichever occurs first.

Total exposure time is defined as the date of first Valchlor exposure to the date of last Valchlor exposure.

Total on-study Valchlor exposure time is defined as the first day of Valchlor use to last day of Valchlor use during the observation period. If the patient was using Valchlor at the end of observation, the last on-study day of Valchlor use is equal to the end date of observation period.

Patients may discontinue Valchlor while on study. In this case, the last day of Valchlor exposure will be when the patient discontinues Valchlor (as reported on the Valchlor treatment log). Patients who restart Valchlor after discontinuing will then begin adding Valchlor exposure days once Valchlor is restarted through the end of the study. For the patients that restart Valchlor during the study, the Total on-study Valchlor exposure will be a sum of all days in which Valchlor was dosed during the study, as reported on the Valchlor treatment log.

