5 RESEARCH METHODS

5.1 Study design

This is a multi-center, prospective, observational study of MF-CTCL patients who have newly initiated Valchlor or who are continuing treatment with Valchlor.

Patients will be followed by their physician according to routine clinical practice. With the exception of protocol-required patient-completed questionnaires, there are no specific or mandated clinical assessments to be performed, and patients will not receive experimental intervention or treatment as a consequence of their participation in this study. The study protocol will not mandate any specific schedule of visits. Patients will undergo clinical assessments and receive standard medical care as determined by the patient's physician in a real-world setting.

Patients will be followed prospectively for a maximum of 2 years from the date of signed informed consent until end of study (EOS), which includes withdrawal of consent, loss to follow-up, death, or study completion. Continuation in the study is not contingent on continuation of Valchlor.

The study will end after all enrolled patients have been followed for 2 years, or discontinued from the study for any reason.

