5.3.2 Exposure definition and measures

Start of observation is defined as date of signed informed consent.

End of observation is defined as EOS, including death, withdrawal of consent, loss to follow-up, or study completion, whichever occurs first.

Total exposure time is defined as the date of first Valchlor exposure to the date of last Valchlor exposure.

Total on-study Valchlor exposure time is defined as the first day of Valchlor use to last day of Valchlor use during the observation period. If the patient was using Valchlor at end of observation, the last on-study day of Valchlor use is equal to the end date of observation period. Drug holidays are excluded from the sum of exposure time.

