5.4 Data sources

Data elements to be collected include the following: patient demographics, personal and family medical history, including MF-CTCL diagnosis date and etiology, current and historical MF-CTCL treatments, clinical status (as assessed by the physician), and which assessments were used to define response, MF-CTCL-related healthcare utilization (as assessed by the physician), AEs and SAEs whether or not related to Valchlor, deaths, patient-completed symptoms and QOL questionnaires. [Table 1](#) provides an overview of the variables collected at enrollment and during the observation period [see [Section 5.3.2](#) for definition]. For patients who do not have any visits, an affirmative response that the patient is still under care by the site will be requested quarterly, so that the absence of reported assessments can be interpreted the same as the absence of actual assessments.

Since this is a real-world, observational study, there are a number of sources of bias that could potentially affect any conclusions that may be drawn. The methods used to minimize these sources of bias in this study are detailed below [see [Section 5.9](#)].

Therapies specific to MF-CTCL during the course of this study are under the direction of the participating physician and not the study protocol. As this study collects data on both incident patients and prevalent patients, it is necessary to include the date of diagnosis in the data collection forms, in order to minimize potential survivor bias effect.

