7.2 Secondary exposures, AE and SAE reporting to Actelion US Drug Safety

All reports of secondary exposures and all AEs will be recorded on the eCRFs and captured in the EDC clinical database. The AE data will be forwarded to Actelion US Drug Safety at predetermined intervals.

All SAEs (including secondary exposures) which occur after initiation of Valchlor treatment until 30 days after Valchlor discontinuation must be collected, recorded and reported during the study. New AEs and SAEs that occur more than 30 days after the discontinuation of Valchlor will be reported to Actelion US Drug Safety if the investigator assesses that there is a possible causal relationship with Valchlor. The minimum information required for collecting and forwarding an SAE to Actelion US Drug Safety is the product name, patient identifier, reporter contact information, and the identified SAE. All SAEs must be recorded on an AE/ADR Form. Cases of secondary exposure must be recorded on the Secondary Exposure Form and submitted directly to Actelion US Drug Safety. The AE/ADR Form will be pre-populated with the information already entered in the eCRF, and it is the physician's responsibility to complete, print, and sign the form and forward to Actelion US Drug Safety directly, within 1 working day

of the investigator's first knowledge of the event, by fax or using the drug safety email address:

[contact]
Actelion US Drug Safety: [contact]

Actelion US Drug Safety will acknowledge the receipt of the AE/ADR form and provide a Manufacturer's Control Number (MCN – a unique number assigned by Drug Safety's database to the case) to the investigator and the Actelion Operations (Clinical Study Leader) within 48 hours. If no acknowledgement is received from Actelion US Drug Safety, the investigator must follow up immediately (or within 1 working day) with a phone call or email to Actelion US Drug Safety to ensure the AE/ADR Form has been received.

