Completing 12 months	N (%)
Completing 15 months	N (%)
Completing 18 months	N (%)
Completing 21 months	N (%)
Completing 24 months	N (%)

Run Date: ddMMMyyyy

Date of Data Extraction: ddMMMyyyy

Helsinn Therapeutics (US), Inc.,  
 Protocol AC-079A501 (PROVe)  
 Table 1B. Completed Visits

Patient Count (n=x)	Enrollment	Ongoing	Early Termination
	x	Visit 1 = x (%)	x
		Visit 2 = x (%)	Patient Withdrew Consent = x (%)
		Visit 3 = x (%)	Patient Lost to Follow-Up = x (%)
		Visit 4 = x (%)	Adverse Event = x (%)
		Visit 5 = x (%)	Physician's Decision to Withdraw = x (%)
		Visit 6 = x (%)	Missing data = x (%)
		Visit 7 = x (%)	
		Visit 8 = x (%)	
		Visit 9 = x (%)	
		Visit 10 = x (%)	
		Visit 11 = x (%)	
		Visit 12 = x (%)	
		Visit > 12 = x (%)	

Run Date:  
 ddMMMyyyy  
 Date of Data Extraction: ddMMMyyyy

Table 1C. Exposure Duration to Valchlor and Other MF-CTCL Therapies

Patient Count = N Number of Patients x (%)	Number of Patients Received 3 months Treatment	Number of Patients Received 6 months Treatment	Number of Patients Received 9 months Treatment	Number of Patients Received 12 months Treatment	Number of Patients Received 15 months Treatment	Number of Patients Received 18 months Treatment	Number of Patients Received months Treatment
Valchlor							
SKIN DIRECTED THERAPIES:							
Phototherapy UVB							
Phototherapy nbUVB							
Phototherapy PUVA							
Radiation Therapy, local, localized electron beam radiation							
Radiation therapy, local TSEBT							
Chemotherapy, topical, Carmustine, topical (BICNU)							
Chemotherapy, topical Other							
Corticosteroids, topical							
Retinoids, Topical Bexarotene (Targretin)							
Retinoids, Topical, Tazarotene (Tazorac, others)							

Retinoids, Topical, Other							
Topical imiquimod (Aldara, others)							
Other topical: specified							
SYSTEMIC THERAPIES:							
Chemotherap y, systemic, Bortezomib (Velcade)							
Chemotherap y, systemic, Chlorambucil (Leukeran)							
Patient Count = N Number of Patients x (%)	Number of Patients Received 3 months Treatment	Number of Patients Received 6 months Treatment	Number of Patients Received 9 months Treatment	Number of Patients Received 12 months Treatment	Number of Patients Received 15 months Treatment	Number of Patients Received 18 months Treatment	Number of Patients Received months Treatment
Chemotherap y, systemic, Cyclophospha mide (Cytoxan, others)							
Chemotherap y, systemic, Doxorubicin, liposomal (Doxil)							

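### The SAP drops death from its end-of-observation definition, termination reasons and stop-date rule, and replaces the protocol's death frequency with a listing of fatal SAEs

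*SAP*

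**What the plan says.** **Protocol.** Section 5.3.2 states: "End of observation is defined as EOS, including death, withdrawal of consent, loss to follow-up, or study completion, whichever occurs first". The synopsis and section 5.1 say the same. Section 5.4 lists the data to be collected as including "AEs and SAEs whether or not related to Valchlor, deaths, patient-completed symptoms and QOL questionnaires", so deaths stand apart from AEs and SAEs. Section 5.7.5 plans the number and percentage of patients with on-study AEs, SAEs or death. Section 5.8 names death among the key data points for central monitoring. Section 5.1 adds: "Continuation in the study is not contingent on continuation of Valchlor".

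**SAP.** Under Exposure Definitions and Measures, the end of study is an event "which includes, adverse event, patient withdrew consent, patient lost to follow-up", followed by physician's decision to withdraw and study completion, whichever is first. The early-termination column of Table 1B opens with "Patient Withdrew Consent = x" and "Patient Lost to Follow-Up = x", then gives adverse event, physician's decision and missing data. For a missing Valchlor stop date, the SAP covers adverse event, loss to follow-up, withdrawn consent and physician's decision. Statistical Methods plans counts of AEs and SAEs and a listing of SAEs with fatal outcome (Listing 2). For disposition, "a listing of all patient disposition, including completed patients and discontinued patients, will be provided" (Listing 6).

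**The concern.** In a lymphoma cohort with no exclusion criteria and table shells running to stage IVB, deaths during up to two years of follow-up are to be expected. A disposition table with no place for death puts those patients under some other reason. A death coded as adverse event then looks like a non-fatal withdrawal, and one coded as lost to follow-up is not visible as a death at all.

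Three things are at stake:
- The protocol's planned summary of on-study death has no counterpart in the SAP.
- The SAP gives no date that ends follow-up for a patient who dies. That date feeds the follow-up time under the hospitalization and ER rates, the person-months in Table 1A, and the last on-study day of Valchlor for a patient still using it.
- Patients stay in the study after stopping Valchlor, so deaths can occur well after treatment. The documents disagree on whether events in that period are collected when judged unrelated.

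**Working it through.** No formula applies. The check compares the passages and then follows a death through the planned outputs.

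**1. End-of-observation events**

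| Event | Protocol 5.3.2 | SAP definition | Table 1B early termination | SAP missing stop-date rule |
|---|---|---|---|---|
| Death | yes | no | no | no |
| Withdrawal of consent | yes | yes | yes | yes |
| Loss to follow-up | yes | yes | yes | yes |
| Adverse event | no | yes | yes | yes |
| Physician's decision | no | yes | yes | yes |
| Study completion | yes | yes | not applicable | not applicable |

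The protocol names 4 events. The SAP removes 1 (death) and adds 2 (adverse event, physician's decision): 4 − 1 + 2 = 5. Table 1B has four of these plus missing data. Death is absent from all three SAP places, so this is not a slip in one list.

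**2. Death outputs.** Protocol 5.7.5 plans a frequency that includes death. The SAP counts AEs (Table 18) and SAEs (Table 19) and lists fatal SAEs (Listing 2). No SAP table counts deaths from any cause.

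**3. Collection more than 30 days after Valchlor**
- Protocol Table 1 footnote, repeated in the SAP Table 1 footnote: safety data are collected up to 30 days after discontinuation; ongoing events are followed to end of study; later new events are reported if possibly related.
- Protocol 7.1.2: later new events are exempt from reporting unless a causal link is reasonably possible.
- Protocol 7.2 opens its rule with "New AEs and SAEs that occur more than 30 days after the discontinuation of Valchlor will be reported to Actelion US Drug Safety if the"; the condition that completes it is a possible causal link in the physician's judgment.
- SAP, Assessment Schedule: related and unrelated AEs and SAEs, including those more than 30 days after discontinuation, are collected at follow-up visits.

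The last statement contradicts the SAP's own footnote as well as the protocol passages.

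**4. Following a death through the outputs**

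| Death | Table 19, Listings 1 and 2 | Table 1B and Listing 6 |
|---|---|---|
| On Valchlor or within 30 days | yes, as a fatal SAE | patient appears; no death reason |
| After 30 days, possibly related | yes | patient appears; no death reason |
| After 30 days, unrelated, outcome of an event already ongoing | yes, since ongoing events are followed to end of study | patient appears; no death reason |
| After 30 days, unrelated, new event | yes under the Assessment Schedule text; not assured under the footnotes and protocol 7.1.2 and 7.2 | patient appears; no death reason |

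The right-hand column is the same in every row. Only the last row depends on which collection rule was applied.

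**5. Direction.** Deaths counted through fatal SAEs equal all deaths minus those never recorded as SAEs. The subtracted number is zero or more, so any error lowers counted mortality. Its size is unknown.

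**The case against.** Several points against the concern are sound.

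- A reader might infer that late, unrelated deaths appear in no planned output. The documents do not support that. The SAP's Assessment Schedule says such events are collected, Listing 2 has no limit on timing or relatedness, and Listing 6 covers every patient. Protocol 5.6.1 also has AEs and SAEs entered in the eCRF whether or not related, and the quoted sentence in 7.2 governs reporting to the safety department. This establishes a conflict between rules, not a proven gap.
- A reader might infer that the SAP ends observation when an adverse event stops Valchlor. It does not. The Analysis Populations section says patients stayed on study after permanent discontinuation for any reason, and the exposure section provides for stopping and restarting. The wording needs clarifying, no more.
- The protocol still ends observation at death, and the SAP list is introduced as inclusive, so a programmer with both documents could apply the protocol.
- The protocol synopsis, unlike 5.7.5, mentions only AE and SAE frequencies and listings that include fatal SAEs. The SAP follows the synopsis.
- Mortality is not a stated objective, and no primary or secondary endpoint is defined by death.

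These points limit the claim but do not remove it. No SAP passage supplies a death category, an end date at death or an all-cause count. Nor can the Assessment Schedule text settle the collection question: the SAP is dated November 2019, after the planned last visit in Q3 2019, so it cannot create records at sites that followed the protocol's 30-day window.

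**Conclusion.** The concern holds in this form. The SAP omits death from its end-of-observation definition, its termination reasons and its stop-date rule, and reduces the planned frequency of on-study death to a listing of fatal SAEs. Followed as written, it codes deaths under another reason and yields no all-cause count. Whether a new, unrelated death more than 30 days after Valchlor is listed at all depends on contradictory rules that must be reconciled.

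The direction is known: an omission can only lower counted mortality. The size is not, because the documents give no death count. A reader might try to size it from the SAP's 15–20% of patients who stopped and switched. That figure counts discontinuations, not deaths, and has no stated denominator. Follow-up after stopping also varies, since patients who had completed one year under the original protocol were not extended to two.

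The conclusion assumes that the Table 1B shell shows all the termination reasons to be tabulated. It should be corrected before results are reported, but it does not threaten the BSA response endpoints.

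**What to change.** 1. Restore death to the SAP's end-of-observation definition, with the date of death as the end date, and add death to the missing stop-date rule.
2. Add a death row to Table 1B and a death reason to Listing 6.
3. As a clarification only, reword adverse event in the definition as withdrawal from the study because of an adverse event, in line with protocol 5.1 and the SAP's Analysis Populations section.
4. Add one all-cause count and listing of on-study deaths, regardless of relatedness or time since Valchlor, split at 30 days after last Valchlor, from the deaths collected under protocol 5.4. State that a death on the end date counts as on-study, because 5.7.5 defines on-study events as falling before the date of leaving the study.
5. Reconcile the SAP's Assessment Schedule with the Table 1 footnotes in both documents and with protocol 7.1.2 and 7.2, and state which collection rule was applied.

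The cost is a definition, a row and a count. One check comes first: Table 1 in both documents has no separate entry for death, so confirm that dates of death are in the database. The downside is a possibly less favourable mortality figure.
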